6.3.3 Follow-up

The Investigator must record follow-up information by updating the medical records and the appropriate forms in the (e)CRF. The worst case severity and seriousness of an event must be kept throughout the trial.

SAE follow-up information should only include new (e.g. corrections or additional) information and must be reported within 24 hours of the Investigator's first knowledge of the information. This is also the case for previously non-serious AEs which subsequently become SAEs.

- All **SAEs** must be followed until the outcome of the event is 'recovered', 'recovered with sequelae', 'not recovered' (in case of death due to another cause) or 'death' (due to the SAE) and until all related queries have been resolved.
- **Non-serious AEs** must be followed until the end of the follow-up period, and until all related queries have been resolved.

SAEs after the end of the trial: If the Investigator becomes aware of an SAE with suspected causal relationship to the trial product or experiment after the subject has ended the trial, the investigator should report this SAE within the same timelines as for SAEs during the trial.

6.3.4 Pregnancy

Female subjects must be instructed to notify the investigator immediately if they become pregnant during the trial. The investigator must report any pregnancy in subjects who have received trial product(s), as soon as possible using an SAE form.

6.3.5 Technical Complaints

Technical complaints should be reported to the Market Authorisation Holder.

6.4 Reporting requirements to Ethics Committee's and Health Authorities

The investigator is responsible for ensuring that all safety events are recorded in the (e)CRF and reported to the Sponsor in accordance with instructions provided below:

Who reports	What	To	Within which period
Investigator	AE	(e)CRF	Cfr protocol

Investigator	SAE (including death) AESI Pregnancy	Coordinating Investigator / sponsor	Immediately (within 24 hours of becoming aware of the event) Exceptions: cfr protocol
PI / sponsor	Each death of a subject from a Belgian site	Central EC	Immediately
PI (Belgian site)	Each death of a subject from an external Belgian site	Local EC	Immediately
PI (non- Belgian site)	Each death of a subject from an external non-Belgian site	According to local legislation	According to local legislation
PI / sponsor	Any SUSAR that is fatal or life- threatening	- Competent Authorities - All other member states if applicable - EC - Investigators - Marketing Authorisation Holder if applicable	Within 7 calendar days, every additional information within additional 8 calendar days
PI / sponsor	All other SUSAR's		Within 15 calendar days
PI / sponsor	Report of all SAE's	Competent Authorities	Annually or final report
		All other member states if applicable	Annually or final report
		EC	Annually a summary of the past year with a safety analysis and risk-benefit evaluation

The Sponsor will promptly evaluate all serious adverse events and adverse events of special interest against experience to identify and expeditiously communicate possible new safety findings to investigators, ECs and applicable health authorities based on applicable legislation.

7 Statistics and Data Analysis

7.1 Sample Size

Based on an estimated IAA incidence of 25% and considering a 80% reduction of the incidence (to 5%) caused by posaconazole prophylaxis and a power of 80%, a sample size calculation showed that 47 patients in each study arm are needed. Because it is impossible that the use of posaconazole will increase the

incidence of IA, a one-sided p-value was used for this sample size calculation. To include at least 100 patients in the MITT endpoint analysis, 110 patients will be included in the study (55 in each arm).

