2.2 Primary Endpoints

The incidence of IAA-infection at ICU discharge is the **primary endpoint** and will be compared for patients receiving posaconazole prophylaxis with those receiving standard of care.

A patient with **IAA-infection** is defined as a patient having mycological evidence of *Aspergillus* and at least one *Aspergillus* compatible sign or symptom and radiological abnormalities (other than interstitial infiltrates) based on chest CT, or chest X-Ray when CT imaging is not available. Mycological evidence can be provided by either (A) a positive culture of *Aspergillus* cultured from BAL sample, (B) ≥ 2 positive cultures of *Aspergillus* cultured from a sputum or a bronchial aspirate or (C) a galactomannan (GM) optical density of ≥ 1 in BAL or ≥ 0.5 in serum. Galactomannan antigen detection is conducted through sandwich enzyme-linked immunosorbent assay (ELISA) (Platelia Aspergillus; Bio-Rad Laboratories, Marnes-la-Coquette, France) and will be performed according to the instructions of the manufacturer. For the isolation of fungi, lower tract respiratory samples will be inoculated on a Sabouraud agar (2 days at 37°C and another 19 days at 30°). *Aspergillus* species are identified by their culture characteristics and morphologies.

Aspergillus compatible signs or symptoms are defined as at least one of the following:

- Worsening respiratory insufficiency in spite of proper antibiotic and ventilator support
- Dyspnea
- Haemoptysis

- Fever refractory to at least 3 days of appropriate antibiotic therapy. Recrudescent fever after a period of defervescence of at least 48 h while still on AB without apparent cause.

The presence of hyphae in lung biopsy or autopsy are also considered as sufficient evidence for IAA.

An independent review committee, consisting of a clinician and a microbiologist with substantial expertise in invasive fungal infections, will evaluate at the end of the study whether IAA-infection is present, based on the above mentioned criteria.

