2.3 Secondary Endpoints

[figure not shown]
Secondary outcomes will be time to IAA diagnosis, length of ICU stay, length of hospital stay, **30-day mortality** and 90-day mortality.

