2.4 Trial Design

This study is an interventional non-blinded randomized controlled multicenter study.

- Critically ill patients with PCR-confirmed influenza (for details: see inclusion criteria) are eligible for inclusion in this study and will be randomized to or the posaconazole prophylaxis group or the SOC group. Within 48 hours after influenza diagnosis with a bronchoscopy with BAL (minimum volume of 2x20mL, 0.9% NaCl) and a with a serum galactomannan will be performed as part of routine ICU care in this type of patients. As any bronchoscopy, this bronchoscopy will only be performed if the safety of the patient will not be compromised. If an IAA-infection is suspected based on the result of this BAL ((A) *Aspergillus* cultured from BAL, or (B) a galactomannan (GM) ≥ 1 in BAL or ≥ 0.5 in serum), the patient will be withdrawn from the study and antifungal treatment will be started. The type and duration of antifungal therapy will be at the discretion of the treating physician.
- SOC further includes:
 - The treating physician can decide to perform an additional bronchoscopy with BAL between day 2 after randomisation and ICU discharge in case of respiratory deterioration and clinical suspicion of an IAA-infection. Any bronchoscopy will only be performed if the safety of the patient will not be compromised. In case of positive mycological evidence of an IAA-infection, a CT thorax without IV contrast is performed if possible. If an IAA-infection is documented, antifungal treatment will be started and - in case the IAA-infection is diagnosed before the ending of the study drug - the patient will be withdrawn from the study. Again, type and duration of antifungal therapy will be at the discretion of the treating physician.

- Oseltamivir (non-IMP) will be started at the discretion of the treating physician from the first day of ICU admission as 2*150 mg/day for a duration of 10 days. If oseltamivir had already been started up before ICU admission, oseltamivir treatment will be continued up to a total of 10 days.

*If *Aspergillus* is **only** cultured from sputum (and not from BAL) within the first 48 hours after the influenza diagnosis, the patient will not be withdrawn from the study

3 Trial Medication / Drug

Drug Name	IMP or non-IMP
Posaconazole	IMP

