7.2 Data Analysis

Appropriate statistical tools will be used to test for significance with respect to the primary and secondary endpoints.

Categorical variables will be reported as a percentage and continuous variables as mean \pm standard deviation (SD) or median and interquartile range (IQR), as appropriate. Differences in categorical variables will be assessed using the Chi squared test or the Fischer's Exact test and for the analysis of continuous variables the Student's t test or the Mann-Whitney U test will be used, where appropriate. P values <0.05 are considered significant. Patients that die during the trial duration will also be included in the statistical analysis.

The primary endpoint analysis will consist of a one-sided fisher-exact test in which the proportion of cases of IAA will be compared between both groups. The population included in this analysis will consist of a modified intent to treat population. This MITT population consists of all patients that received at least 1 posaco/placebo administration but excluding the patients in which a diagnosis of IAA was made on the basis of the BAL sample taken on day 1 because these patients in fact had an IAA at the day of inclusion.

8 Data handling

Patient data will be encoded: which means that personal data can only be related to an identified or identifiable person by means of a code.

Demographic, biochemical, microbiological and radiological data will be collected prospectively as a part of clinical routine. Samples will be obtained for characterization of the influenza type and for *Aspergillus* diagnosis including culture, galactomannan and PCR. These samples are part of daily routine, no additional samples for this study will be taken. All *Aspergillus* colonies will be screened for azole resistance, using an agar-based selection tool, and relevant samples, i.e. BAL fluid, will be stored for direct detection of resistance mutations by PCR. Clinical *A. fumigatus* isolates will be sent the National Mycology Reference Laboratory in Leuven (Belgium) or Nijmegen (the Netherlands) for MIC-testing and analysis of azole-resistance mutations. A blinded data review committee following a pre-defined case definition will classify patients with evidence for primary and breakthrough IAA-infection.

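### Section 7.2 plans arm percentages and a one-sided Fisher P for the primary endpoint but no interval for the effect; add a risk difference with its CI, with Boschloo's test as an optional gain

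*Combined protocol and SAP*

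**What the plan says.** Section 7.2 fixes the primary test: "The primary endpoint analysis will consist of a one-sided fisher-exact test" of the IAA proportions in the modified intention-to-treat population. It gives no reason for one-sidedness. On reporting it says "Categorical variables will be reported as a percentage", and on the threshold "P values <0.05 are considered significant". No difference, ratio or confidence interval is planned for any endpoint.

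Section 7.1 derives 47 per arm from 25% vs 5% at 80% power. It enrols 55 per arm so that at least 100 are analysed. It states no alpha. Its reason for a one-sided P is "Because it is impossible that the use of posaconazole will increase the" incidence of IA, and that sentence is written for the sample size calculation.

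The endpoint in section 2.2 is IAA by ICU discharge. On later sampling, section 2.4 says "The treating physician can decide to perform an additional bronchoscopy with BAL between day 2 after randomisation and ICU discharge". Classification is reviewed twice: "An independent review committee, consisting of a clinician and a microbiologist" (section 2.2) and "A blinded data review committee following a pre-defined case definition will classify patients" (section 8).

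**The concern.** Section 2.1 describes the trial as proof of concept. About 50 patients per arm give an imprecise estimate, and how imprecise is what the next study needs to know. Two percentages and a one-sided P do not convey it. A result just under 0.05 and a result showing an excess on posaconazole would both be published without a range of compatible effects. If the interval is chosen after the data are seen, its measure, method and level are all open to choice.

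Two smaller matters sit beside this. Fisher's test is conservative at this size, so some power can be gained without more patients. The stated reason for one-sidedness is also stronger than the design supports.

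**Working it through.** **Inputs.** 25% vs 5%, 80% power, 47 per arm, 55 per arm enrolled and at least 100 analysed (7.1); 50 per arm (synopsis); one-sided Fisher test and P<0.05 (7.2). One-sided alpha of 0.05 is an assumption taken from the general threshold in 7.2.

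**1. The plan's own figure.** With pooled rate 0.15, n = [1.645·√(2·0.15·0.85) + 0.842·√(0.25·0.75 + 0.05·0.95)]² / 0.20² = 38.35, so 39. With continuity correction, n = (38.35/4)·[1 + √(1 + 4/(38.35·0.20))]² = 47.8, so 48. By exact enumeration, one-sided Fisher first reaches 80% at 45 per arm (80.7%) and has 82.7% at 47. The stated 47 is reproduced within 2.

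**2. What an interval adds (50 per arm, posaconazole minus SOC).** For SOC 8 and posaconazole 2:
- Fisher P = Σ C(50,k)·C(50,10−k)/C(100,10) for k = 8 to 10 = 0.046.
- Risk difference = 0.04 − 0.16 = −0.12.
- Wilson 95% limits are 0.0110 to 0.1346 (2/50) and 0.0834 to 0.2851 (8/50).
- Newcombe lower limit: −0.12 − √[(0.04−0.0110)² + (0.2851−0.16)²] = −0.248.
- Newcombe upper limit: −0.12 + √[(0.1346−0.04)² + (0.16−0.0834)²] = +0.002.
- 90% version, with Wilson limits 0.0133 to 0.1139 and 0.0926 to 0.2623: −0.226 to −0.020.

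| SOC vs posaconazole cases | Planned P | Risk difference (points) | 95% CI |
|---|---|---|---|
| 8 vs 2 | 0.046 | −12 | −24.8 to +0.2 |
| 5 vs 0 | 0.028 | −10 | −21.4 to −0.9 |
| 5 vs 12 | 0.98 | +14 | −0.9 to +28.6 |

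Even a result close to the design rates, 12 vs 3, gives −18 points with a 95% CI from −32.0 to −3.9.

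**3. Fisher against Boschloo.** All tables were enumerated. Boschloo's test orders tables by the Fisher P and takes the largest cutoff whose maximum size (type I error maximised over the common rate) stays at or below 5%. At 50 per arm that cutoff is a Fisher P of 0.0698.

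| Per arm, one-sided 0.05 | Fisher power | Boschloo power | Maximum size, Fisher / Boschloo |
|---|---|---|---|
| 47 | 82.7% | 86.1% | 3.9% / 4.8% |
| 50 | 85.3% | 88.4% | 3.3% / 4.9% |
| 55 | 88.9% | 90.9% | 3.5% / 4.99% |

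With 100 analysed and arms split between 48/52 and 52/48, the gain is 2.9 to 5.1 points. If alpha were one-sided 0.025, Fisher's power would be 70.8% at 47 per arm and 74.8% at 50.

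**4. Test and interval together (50 per arm).** Boschloo makes 36 further tables significant. An example is 4 vs 0: Fisher P = C(50,4)/C(100,4) = 230,300/3,921,225 = 0.059, Boschloo P = 0.044, upper 95% limit +0.6 points. All 36 have a 95% CI that includes zero and a 90% CI that excludes it. At 25% vs 5%, the chance of a significant result whose 95% CI includes zero rises from 2.9% with Fisher to 6.1% with Boschloo.

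**5. The rationale.** The claim in 7.1 concerns IA. The endpoint counts diagnosed IAA, with treatment known and later BAL at the physician's discretion. The count therefore also depends on who is sampled and for how long. The review committees can judge only the samples that were taken.

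**The case against.** The strongest reply is that little is hidden. A reader might infer that an unfavourable result would show only as a P near 1. The documents do not support that: 7.2 requires percentages, so 5 vs 12 would appear as 10% vs 24%, and the difference is a subtraction. What stands is narrower: no interval is planned.

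A reader might also infer that the primary test is invalid because its rationale fails. It is not. The sentence in 7.1 is attached to the sample size, 7.2 gives no reason of its own, and a one-sided test can be defended on other grounds. Nor do the documents show that discretionary BAL would raise the posaconazole count; no direction or size is given. Rewording changes no result, and neither the CI nor another test corrects differential sampling.

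Boschloo's test can fairly be called a preference. Fisher's is valid and meets the target at the apparent alpha, and the results that Boschloo adds are the least precise ones. That is why it is optional here.

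Newcombe's interval is approximate and does not mirror an exact test perfectly. At 50 per arm, 10 tables (2.0% chance at 25% vs 5%) have a 90% CI excluding zero without Boschloo significance; with Fisher it is 46 tables (5.2%). The test should decide and the interval describe.

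Finally, a two-sided unpooled formula gives 46.1, so 47, and a reader might infer that the calculation was really two-sided. The text says one-sided, and one-sided methods come within 2, so this is not shown.

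**Conclusion.** The point holds as a gap in reporting. The primary analysis has no planned interval, so the trial as written would not show the range of benefit or excess compatible with its data. The 8 vs 2 case shows the size of this: significant under the plan, yet with a 95% CI reaching +0.2 points.

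The choice of test is a possible gain and not a fault: +3.1 points at 50 per arm and +2.1 at 55 for 25% vs 5%, with maximum size still below 5%. These figures assume one-sided alpha of 0.05 and equal arms. The statement that Fisher meets 80% rests on the same alpha. The wording in 7.1 is a minor matter.

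**What to change.** **7.2, main change.** Pre-specify the risk difference (posaconazole minus SOC) with a two-sided 95% CI and name the method, for example Newcombe. Show the 90% CI beside it, because the test is one-sided at an apparent 0.05. State alpha explicitly here and in 7.1.

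**7.2, optional.** Before data are seen, name Boschloo's exact test in place of Fisher's at the same one-sided 0.05, and restate the power in 7.1 for the named test. Say in the text that significance at this level does not imply a 95% CI excluding zero; 8 vs 2 shows that this sentence is needed with Fisher too.

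**7.1, wording.** Replace the claim of impossibility with a supportable reason, such as proof of concept with interest only in benefit and any excess shown by the CI.

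**Cost.** A few sentences and one software call, with no extra patients or data. With Boschloo, maximum size at 50 per arm rises from 3.3% to 4.9%, and all of the added power comes from results whose 95% CI includes zero. If the sponsor keeps Fisher, the interval, the stated alpha and the 7.1 wording should still change.

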Prinicpal Investigators and Participating Sites	[name]. [name], Intensivist, UZ Leuven [name]. [name], Medical microbiologist, UMC Radboud Nijmegen
Medical condition or disease under investigation	Influenza-associated pulmonary aspergillosis (IAA)
Purpose of clinical trial	Study the effect of antifungal prophylaxis on the incidence of IAA in critically ill patients with severe influenza.
Primary objective	Study if antifungal prophylaxis can decrease the incidence of IAA compared to SOC in critically ill patients with severe influenza pneumonia.
Secondary objective(s)	
Trial Design	Interventional non-blinded randomized controlled multicenter study
Endpoints	The IAA incidence at ICU discharge is the primary endpoint and will be compared in patients receiving posaconazole prophylaxis with those receiving SOC. Secondary outcomes will be time to IAA diagnosis, length of ICU stay, length of hospital stay, 30-day mortality and 90-day mortality
Sample Size	50 patients in each arm
IMP, dosage and route of administration	Posaconazole, 2*300mg/d on day 1, followed by 1*300mg/d from day 2 until day 7, intravenously administrated
Active product(s)	comparator None, SOC
Maximum duration of treatment of a Subject	7 days of prophylaxis

Maximum duration of Trial	4 influenza seasons (the first two influenza seasons will be supported by MSD)
Anticipate First Patient First Visit (FPFV)	Expected 01/12/2017
Anticipate Last Patient Last Visit (LPLV)	Expected 30/03/2021

TRIAL FLOWCHART

Schedule of Events – Trial specific Procedures / Assessments

EVENTS	Screening	Randomization	Treatment Period	ICU discharge	Follow-Up Visits (phone call)
Timing (weeks)		Day 1	Day 2 - ICU discharge		Day 30 and day 90
Informed consent ^a	X				
PCR-confirmed influenza ^b	X				
Inclusion/Exclusion	X	X			
Demographics; Medical history	X				
Symptom directed physical examination	X	X	X	X	
Weight / Height	X				
Vital Signs	X	X	X	X	
Randomization		X			
Microbiology sampling	X	X ^c	X ^d	X	
Chemistry : laboratory measurements	X	X	X	X	
Radiological Assessments (CT / RX)		X	X		
Trial drug administration (max 7 days)		X	X		
IAA mycological evidence ^e	X	X	X	X	X
IAA signs and symptoms assessment	X	X	X	X	
Survival status		X	X	X	X
Adverse event (AE) assessment ^f			→		
Serious Adverse Event (SAE) assessment				→	
Concomitant Medication (CM)					

a: Informed Consent process should take place prior to all other trial-related procedures at the screening visit

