b: On NS, BA or BAL within the last 7 days before ICU admission or within 2 days after ICU admission; or based on a positive rapid test if PCR not available

c: BAL GM, BAL culture and serum GM within 48h after influenza diagnosis to collect mycological evidence for IAA-infection

d: BAL GM, BAL culture and serum GM between day 2 after randomization and ICU discharge, at the discretion of the treating physician, or later during ICU admission in case of clinical respiratory deterioration

e: Provided by either (A) a positive culture of *Aspergillus* cultured from BAL, (B) ≥2 positive cultures of *Aspergillus* cultured from a sputum or a bronchial aspirate or (C) a galactomannan (GM) optical density of ≥1 in BAL or ≥0.5 in serum

f: Study drug related adverse events

I Background and Rationale

Invasive aspergillosis has been regarded as an infectious complication of specific immunocompromised patients, which affects a relatively small group of patients. However, in recent years aspergillus disease has become a prominent problem in ICU-patients.

Influenza-associated aspergillosis (IAA) was recently found to be a frequent and severe complication of influenza pneumonia in critically-ill patients.[1] A retrospective observational study during the 2015/2016 influenza season indicated that among 144 patients admitted to the ICUs of all eight Dutch University Medical Centres with influenza, 23 (16%) developed IAA.[2] The underlying diseases in these patients were diverse, and 7 patients had been previously healthy. A 61% mortality rate was observed, including 5 of 7 previously healthy patients who died.[2] It is thus clear that IAA is an early and frequent complication of severe influenza pneumonia, and that delay in diagnosis and treatment increases the probability of death in these critically ill patients. Early diagnosis is difficult due to unspecific clinical and radiological presentation. [1,2]

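### A low-cost gain, not an error: replacing Fisher's test with Boschloo's exact test in section 7.2, at the same one-sided 5% and the same N, raises power at the plan's 25% vs 5% from 85.3% to 88.4%

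*Combined protocol and SAP*

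**What the plan says.** Section 7.1 sets the design rates: "Based on an estimated IAA incidence of 25% and considering a 80% reduction of the incidence (to 5%) caused by posaconazole prophylaxis". With 80% power and a one-sided test it arrives at 47 per arm. It then adds a margin and labels both figures: "To include at least 100 patients in the MITT endpoint analysis, 110 patients will be included in the study (55 in each arm").

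Section 7.2 names the primary test: "The primary endpoint analysis will consist of a one-sided fisher-exact test". It is applied to a modified intention-to-treat (MITT) population, which is defined by "excluding the patients in which a diagnosis of IAA was made on the basis of the BAL sample taken on day 1". The only significance threshold is a general one in the same section: "P values <0.05 are considered significant". Section 7.1 states no alpha, so one-sided 5% is an inference from the two sections together.

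The sample size row of the synopsis reads "50 patients in each arm", without saying whether that means enrolled or analysed.

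On outcome assessment, section 2.2 says that an independent committee "will evaluate at the end of the study whether IAA-infection is present", and section 8 calls the data review committee blinded. Treatment itself is non-blinded (section 2.4).

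**The concern.** Fisher's test conditions on the total number of events. With few events its p-values are widely spaced, and its true type I error falls well below the nominal level. At the design rates and 50 per arm, about 12.5 IAA cases are expected on SOC (50 x 0.25) and 2.5 on posaconazole (50 x 0.05), so the effect is not negligible. An unconditional exact test can use the unspent part of the 5% without giving up exact error control.

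The choice of test can decide the result in plausible tables. At 50 per arm, these counts (posaconazole vs SOC) fall on opposite sides of 0.05:

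| IAA cases | Fisher p | Boschloo p |
|---|---|---|
| 1 vs 6 | 0.056 | 0.044 |
| 3 vs 9 | 0.061 | 0.044 |
| 5 vs 12 | 0.054 | 0.039 |

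That sensitivity is the reason to settle the test early, and equally the reason that a late change would be suspect.

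A smaller matter is that the unlabelled synopsis row could lead someone working from the synopsis alone to take 100, not 110, as the enrolment target.

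**Working it through.** **Inputs.** SOC rate 25%, posaconazole rate 5%, power 80%, one-sided, 110 enrolled and at least 100 analysed (section 7.1). One-sided Fisher exact test and threshold 0.05 (section 7.2). Sensitivity rate 16% from the background: "23 (16%) developed IAA" among 144 patients. An 80% reduction of 16% gives 0.2 x 16% = 3.2%.

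**Step 1: the plan's 47 per arm.** The normal-approximation formula with pooled variance under the null is

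n = [1.645 x sqrt(2 x 0.15 x 0.85) + 0.842 x sqrt(0.25 x 0.75 + 0.05 x 0.95)]^2 / 0.20^2 = 38.35.

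With continuity correction, n/4 x [1 + sqrt(1 + 4/(n x 0.20))]^2 = 47.83, which is 48 rounded up and 47 truncated. Exact Fisher power by full enumeration is 79.6% at 44 per arm, 80.7% at 45 and 82.7% at 47. So 47 is adequate. At a one-sided 2.5%, Fisher power at 47 per arm would be 70.8%, short of 80%, which supports reading the plan as one-sided 5%.

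**Step 2: the two tests at 50 per arm.** Power is the sum, over all tables in the rejection region, of Bin(x; 50, p1) x Bin(y; 50, p2). Size is the maximum of the same sum over a common rate p1 = p2.

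- Fisher rejects when its one-sided p is at most 0.05. Maximum size 3.3%.
- Boschloo orders tables by the Fisher p-value and takes the largest cut-off that keeps maximum size within 5%. That cut-off is a Fisher p of 0.0698, with maximum size 4.86%. The next attainable cut-off would give 5.10%.

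Boschloo's rejection region contains Fisher's, so its power is never lower.

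| Rates (SOC vs posaconazole), 50 per arm | Fisher | Boschloo | Gain (points) |
|---|---|---|---|
| 25% vs 5% (plan) | 85.3% | 88.4% | 3.1 |
| 16% vs 3.2% (sensitivity) | 60.6% | 67.6% | 7.0 |

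**Step 3: unequal arms, 100 analysed, 25% vs 5%.**

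| SOC/posaconazole | Fisher | Boschloo | Gain (points) |
|---|---|---|---|
| 53/47 | 85.3% | 87.7% | 2.4 |
| 52/48 | 86.0% | 88.9% | 2.9 |
| 51/49 | 84.4% | 89.5% | 5.1 |
| 49/51 | 84.6% | 89.0% | 4.5 |
| 48/52 | 85.0% | 88.8% | 3.8 |
| 47/53 | 84.7% | 88.8% | 4.0 |

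**Step 4: what 3 points are worth.** Fisher reaches 88.2% at 54 per arm and 88.9% at 55. It therefore needs 55 per arm analysed to match Boschloo at 50, which is 10 more analysed patients.

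**Step 5: the synopsis row.** Read as analysed, 50 per arm equals section 7.1's target of 100. Read as enrolled, with section 7.1's own ratio, 100 x 100/110 = about 91 analysed. At 45 per arm Fisher power is 80.7% at 25% vs 5%, still above 80%.

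**The case against.** Fisher's test is prespecified, valid and meets the power target, and a conservative test is not a defect. That stands in full: Boschloo's test is an improvement on offer, not a correction.

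The size of the gain depends on conditions. At the plan's rates and equal arms it is about 3 points, and it falls to 2.1 if all 55 per arm are analysed. It also shifts with the arm split, which is not known in advance. A reader might quote 3 to 7 points as a general range. The documents do not support that, because the 7 needs the 16% cohort rate, which section 7.1 does not adopt.

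The strongest objection concerns timing. The trial is non-blinded. IAA is diagnosed at the bedside during the ICU stay and, if found during prophylaxis, leads to withdrawal (sections 2.4, 4.4 and 5.5.2). Investigators may therefore know approximate IAA counts by arm long before the committee classifies cases. An amendment dated just before that classification could still be made with knowledge of the results, and it would move borderline tables from non-significant to significant. This objection also stands, and it limits when the change can be made.

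**Conclusion.** The point holds as a low-cost improvement. At 50 per arm and one-sided 5%, Boschloo's test uses up to 4.86% of the allowed error where Fisher uses at most 3.3%. It raises power at 25% vs 5% from 85.3% to 88.4%, or by 2.4 to 5.1 points over the uneven splits of 100 checked. Only under the 16% sensitivity rate with the same relative reduction is it 60.6% to 67.6% with equal arms. All of this rests on one-sided 5%, inferred from sections 7.1 and 7.2, and on about 100 patients analysed.

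Three stronger readings are not supported:

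- That 47 per arm is wrong. It reproduces.
- That the synopsis contradicts section 7.1. Its 50 per arm equals the MITT target, and even the adverse reading leaves 80.7% power, so this is a labelling matter.
- That removing day-1 IAA cases leaves the trial underpowered. Section 7.1 does not say whether its rates are counted before or after that removal, and power can move either way depending on the answer. No shortfall is shown.

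**What to change.** In section 7.2, name Boschloo's exact test as the primary test, at one-sided 5% and computed on the actual MITT arm sizes, with the one-sided Fisher test as a sensitivity analysis.

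Make the amendment before any IAA counts by arm are tabulated or known to those deciding it. Ideally this is before or early in enrolment, and the decision is taken by a statistician without access to outcomes by arm. Dating it before the committee's end-of-study classification is not enough. If the condition cannot be met, keep Fisher as primary and report Boschloo as supportive.

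As an editorial change, have the synopsis row read: 110 enrolled (55 per arm), at least 100 in the MITT set.

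The cost is text only, with no added patients or procedures. There are two downsides: the prespecified primary test changes, and more of the nominal 5% is used (a maximum of 4.86% instead of 3.3% at 50 per arm).
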